6.2.3 Prohibited medication

[figure not shown]
Use of the treatments displayed in the below table are not allowed during the specified time period.

Table 6-3 Prohibited medication

Medication	Prohibition period	Action taken
Biologics for treatment of CSU (including omalizumab and ligelizumab)	4 months prior to randomization until end of treatment	Discontinue biologic treatment and closely monitor for potential associated adverse events.

Medication	Prohibition period	Action taken
Routine (more than 3 doses over a 5 day period) oral corticosteroids	30 days prior to screening until end of treatment Oral corticosteroids are only allowed as an additional rescue therapy for CSU AFTER Week 12 , on an as-needed basis for unbearable symptoms as per Section 6.2.4 . Other preparations of corticosteroids (CS) with limited systemic exposure for non-CSU indications (e.g., intra-nasal or any topical CS) can be used on an as-needed basis.	Discontinue routine corticosteroids if medically justifiable and closely monitor for potential associated adverse events. If discontinuation of routine corticosteroids is not possible, discontinue study treatment.
i.v./IM/IA corticosteroids	30 days prior to screening until end of treatment	Discontinue i.v./IM/IA corticosteroids if medically justifiable and closely monitor for potential associated adverse events. If discontinuation of i.v./IM/IA corticosteroids is not possible, discontinue study treatment.
Leukotriene antagonists (including montelukast and zafirlukast)	From screening until end of treatment	Discontinue Leukotriene antagonists and closely monitor for potential associated adverse events.
H2-antihistamines	From screening until end of treatment	Discontinue H2-antihistamines and closely monitor for potential associated adverse events.
First generation antihistamines	From screening until end of treatment	Discontinue first generation antihistamines and closely monitor for potential associated adverse events.
Second generation antihistamines other than the participant's defined background medication and rescue medication	From 7 days prior to randomization until end of treatment	Discontinue all second generation H1-antihistamines but the defined background and rescue medication and closely monitor for potential associated adverse events.

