Other immunosuppressive/immunomodulating medication with or without known effect on CSU including but not limited to hydroxychloroquine, methotrexate, cyclosporine A, cyclophosphamide, tacrolimus and mycophenolate mofetil	30 days or 5 half-lives (whichever is longer) prior to screening until end of treatment	Discontinue immunosuppressive/immunomodulating medication if medically justifiable and closely monitor for potential associated adverse events. If discontinuation not possible, discontinue study treatment.

Medication	Prohibition period	Action taken
Intravenous (i.v.) immunoglobulins or plasmapheresis	30 days prior to screening until end of treatment	Discontinue i.v. immunoglobulins or plasmapheresis if medically justifiable and closely monitor for potential associated adverse events. If discontinuation not possible, discontinue study treatment.
UV therapy	From screening until end of treatment	Discontinue UV therapy and closely monitor for potential associated adverse events.
Any other therapy intended for the treatment of urticaria including but not limited to herbal therapies	From 2 weeks prior randomization until end of treatment	Discontinue any therapy intended for the treatment of urticaria and closely monitor for potential associated adverse events.
Live attenuated vaccines	6 weeks prior to randomization until at least 4 weeks after the last dose of study treatment	Discontinue study treatment.
Strong inhibitors of CYP3A4	From 2 weeks prior randomization until end of treatment	Discontinue CYP3A4 inhibitor if medically justifiable and closely monitor for potential associated adverse events. If discontinuation not possible, discontinue study treatment
Moderate and strong inducers of CYP3A4	From 2 weeks prior randomization until end of treatment	Discontinue CYP3A4 inducers if medically justifiable and closely monitor for potential associated adverse events. If discontinuation not possible, discontinue study treatment.

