1.2.1 Primary estimand(s)

The estimand is the precise description of the treatment effect and reflects strategies to address events occurring during trial conduct which could impact the interpretation of the trial results (e.g. premature discontinuation of treatment).

Primary estimand for scenario with UAS7 as primary efficacy endpoint

The primary clinical question of interest is: What is the effect of remibrutinib treatment versus placebo on the change from baseline in UAS7 score after 12 weeks treatment in adult participants with CSU who are inadequately controlled by H1-antihistamine and receiving a stable locally label approved dose of a second generation H1-antihistamine, regardless of discontinuation from study treatment for any reason and regardless of intake of a different second generation H1-antihistamine as rescue medication and considering strongly confounding prohibited medication as an unfavourable outcome?

The primary estimand is described by the following attributes:

1. **Population:** participants with inadequately controlled CSU despite treatment with second generation H1-antihistamine who have CSU duration \geq 6 months, a UAS7 score \geq 16, ISS7 \geq 6 and HSS7 score \geq 6 in the last 7 days prior to randomization.
2. **Endpoint:** Change in UAS7 from baseline at Week 12.
3. **Treatment of interest:** the randomized study treatment (remibrutinib 25 mg b.i.d. or placebo) regardless of treatment compliance, with background medication of locally label approved dose second generation H1-antihistamine, and a different second generation H1-antihistamine as rescue medication.
4. **Summary Measurement:** the mean difference between treatment groups.
5. **Handling of intercurrent events:**
 - Discontinuation of study treatment due to any reason: Treatment policy strategy
 - Intake of strongly confounding prohibited medication (e.g. biologics treatment at any time before Week 12, cyclosporin after Week 8, systemic corticosteroids after Week 8): Composite strategy (irrespective of potential occurrence of other intercurrent events)
 - Intake of rescue medication, switch of background medication, intake of other prohibited medication, or participants non-compliant to treatment prior to Week 12: Treatment policy strategy

Primary estimand for scenario with ISS7/HSS7 as co-primary efficacy endpoints

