	Week 37	-	Day 85 to Day 91 of open-label period
	Week 38	-	Day 92 to Day 98 of open-label period
	Week 39	-	Day 99 to Day 105 of open-label period
	Week 40	281	Day 106 to Day 112 of open-label period
	Week 41	-	Day 113 to Day 119 of open-label period
	Week 42	-	Day 120 to Day 126 of open-label period
	Week 43	-	Day 127 to Day 133 of open-label period
	Week 44	-	Day 134 to Day 140 of open-label period
	Week 45	-	Day 141 to Day 147 of open-label period

	Week 46	-	Day 148 to Day 154 of open-label period
	Week 47	-	Day 155 to Day 161 of open-label period
	Week 48	-	Day 162 to Day 168 of open-label period
	Week 49	-	Day 169 to Day 175 of open-label period
	Week 50	-	Day 176 to Day 182 of open-label period
	Week 51	-	Day 183 to Day 189 of open-label period
	Week 52	365	Day 190 to Day 196 of open-label period
No further analysis visit			

Assessment window for the assessments performed at study visit (e.g. DLQI, [REDACTED], safety assessment except AEs etc.) until Week 52

When the assessments are summarized by visit, they are based on the visit numbers as recorded in eDiary or eCRF except for end of treatment (ETD) visit, and study discontinuation (SD) visit. **ETD visit, SD visit** will be remapped to the scheduled visit. Safety follow-up visit or unscheduled visits will NOT be remapped (except for the unscheduled visit to be considered as baseline).

The assessment window is based on the study assessment schedule. For participants initially randomized to placebo and switched to LOU064, the date of first OL study treatment will be considered. The assessments under placebo treatment will not be remapped to the visits during OL period and the assessments under LOU064 treatment will not be remapped to the visits during DB period.

The protocol defined assessment schedule is shown in [Table 2-6](#). For ECG, at Week 2, 12, 52 and SD visit pre and post-dose assessments will be collected. ETD visit can be remapped to Week 24 only, and SD visit can be remapped to Week 2, 12 and 52.

Table 2-6 Assessment schedule

Visit Name	BSL	week 2	week 4	week 8	week 12	week 16	week 20	week 24	week 32	week 40	week 52	ETD	SD
Scheduled visit Day	1	15	29	57	85	113	141	169	225	281	365	-	-
Vital Signs													
Clinical Chemistry*	X	X	X	X	X	X	X	X	X	X	X	X	X
Hematology													
Urinalysis													
Coagulation Panel	X		X		X			X		X	X	X	X
Weight					X						X	X	X
ECG	X	X ²			X ²			X			X ²	X	X ²
DLQI	X		X		X			X			X	X	X

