2.5.1.3 Handling of intercurrent events

Participants who discontinue from study treatment early due to any reason will be encouraged to stay in the study following the procedures. Every effort will be made to continue to follow participants who discontinued from study treatment up to Week 12. These are considered as Retrieved drop out (RDO) participants.

The analysis will account for different intercurrent events as explained in the following:

1. Discontinuation of study treatment prior to Week 12 due to any reason:

A treatment policy strategy will be applied and these intercurrent events will be ignored. Data collection will be maintained and available measurements post-treatment discontinuation will be used as if they had been obtained under the treatment assigned at randomization. i.e, RDO data collected after study treatment discontinuation will be used for analysis. In case of missing values, a multiple imputation approach will be applied (see [Section 2.5.1.4](#) for details).

2. Intake of rescue medication as per protocol, or switch of background medication, or intake of other prohibited medication (except for strongly confounding prohibited medication listed below), or participants non-compliant (dose interruption) to treatment prior to Week 12:

A treatment policy strategy will be applied in the same way as described above. Data collected after these events will be used for analysis.

3. Intake of strongly confounding prohibited medication:

- Biologics treatment at any time before Week 12 (as identified by PD M-COMD03)
- Cyclosporin after Week 8 to Week 12 (as identified by PD M-COMD04)
- Systemic corticosteroids after Week 8 to Week 12 (as identified by PD M-COMD04)

A composite strategy will be applied. Measurements after this event will be excluded from the analysis and will be imputed using the worst value of the endpoint (i.e., 42 for UAS7).

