2.5.1.4 Handling of missing values

Missing data imputation will be performed for the analyses when using statistical model.

Handling of missing RDO data

If no RDO data was collected after study treatment permanent discontinuation, missing data will be imputed based on the following rules:

- For participants in the active treatment arms, if sufficient RDO data, missing data will be imputed using MI based on observed RDO data in the corresponding active arm. If not feasible (e.g., very limited RDO data), missing data will be imputed based on observed data in the placebo arm under the assumption of jump to reference (J2R) using MI.
- For participants in the placebo arm, if sufficient RDO data, missing data will be imputed using MI based on observed RDO placebo arm data. If not feasible (e.g., very limited RDO data), missing data will be imputed using MI under the MAR assumption based on the observed placebo arm data.

Handling of other missing data

If there is any missing data prior to Week 12, the missing data will be handled following the MAR assumption.

The detailed steps for handling of the intercurrent events and analyses are described below.

Step 1: Identify the participants with intercurrent events.

Step 2: For participants with intercurrent event 1 (Discontinuation of study treatment prior to Week 12 due to any reasons), determine the imputation strategy based on the amount of RDO data.

- Calculate the percentage of RDO data available at Week 12 in participants with intercurrent event 1 by treatment group
- If $\geq 50\%$ of participants had RDO data at Week 12, consider RDO data is sufficient
- If $< 50\%$ of participants had RDO data at Week 12, consider RDO data is not sufficient

Step 3: Perform the missing data imputation.

- For participants with intercurrent event 3 (Intake of strongly confounding prohibited medication), set missing at all visits after the event
- Perform the missing data imputation under MI framework according to the imputation strategy on Step 2. At the same time, missing data imputation of other missing data (i.e., non RDO data) will also be performed. The details on MI are described in [Section 5.4.3](#)

- Replace the values at all visits after the intercurrent event 3 with the worst value

Step 4: Perform the analysis.

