3.1 Primary endpoint(s)

In order to fulfill registration and ICH E1 requirements on the number of participants treated for 6 months and 12 months in the development program, a sample size of 300 participants in the active arm and 150 in the placebo arm is targeted. Hence, the total sample size is 450 randomized participants.

From an efficacy point of view, the sample size justification is based on UAS7 change from baseline (for scenario with one primary endpoint), ISS7 and HSS7 change from baseline (for scenario with co-primary endpoints) and achievement of $UAS7 \leq 6$ and $UAS7 = 0$ at Week 12. To avoid assigning an unnecessary large number of participants to placebo, participants will be randomized in a 2:1 ratio to remibrutinib 25 mg b.i.d. and placebo arms, respectively.

All calculations were performed with nQuery Advisor 8.4.1.0 and Ri386 4.0.2 softwares.

For scenario with UAS7 as the primary efficacy endpoint

UAS7 change from baseline at Week 12

Approximately 10% drop-out is expected at week 12, thus with 270 participants in the active arm and 135 participants in the placebo arm, this gives a nominal power of more than >99% to detect a difference between remibrutinib and placebo if the mean change of UAS7 from baseline to Week 12 is at least 10 in favor of remibrutinib, with common standard deviation of approximately 12 (based on the primary endpoint analysis of Phase 2b study (CLOU064A2201)), based on a t-test, assuming type I error 0.025 (one-sided).

For scenario with ISS7/HSS7 as the co-primary efficacy endpoints

ISS7 change from baseline at Week 12

Approximately 10% drop-out is expected at week 12, thus with 270 participants in the active arm and 135 participants in the placebo arm, this gives a nominal power of more than >99% to detect a difference between remibrutinib and placebo if the mean change of ISS7 from baseline to Week 12 is at least 4 in favor of remibrutinib, with common standard deviation of approximately 6 (based on the primary endpoint analysis of Phase 2b study (CLOU064A2201)), based on a t-test, assuming type I error 0.025 (one-sided).

HSS7 change from baseline at Week 12

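### The composite intercurrent event is identified only by deviation code, so a confounding drug started after study drug is stopped early may be missed

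*SAP*

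**What the plan says.** - **Detection rule.** SAP 2.5.1.3 lists three strongly confounding medications and ties each to a deviation code. For biologics the entry is "Biologics treatment at any time before Week 12 (as identified by PD M-COMD03". Cyclosporin and systemic corticosteroids count only from Week 8 to Week 12 and are tied to M-COMD04. No other means of identification is given. Values after the event are replaced by the worst score (42 for UAS7).
- **Scope of the estimand.** SAP 1.2.1 assigns this event a "Composite strategy (irrespective of potential occurrence of other intercurrent events". Protocol 12.4.3 defines the event by intake and mentions no deviation code. SAP Section 4 reports no change from the protocol.
- **Prohibition periods.** Protocol Table 6-3 bans urticaria biologics "4 months prior to randomization until end of treatment" and cyclosporine with other immunosuppressants "30 days or 5 half-lives (whichever is longer) prior to screening until end of treatment". The rows for routine oral and for i.v./IM/IA corticosteroids stop at the same point. The live-vaccine row, by contrast, runs at least 4 weeks past the last dose.
- **Meaning of the end point.** Neither document defines end of treatment. In its visit-remapping rule, SAP 2.1.1.5 attaches the phrase to the early-discontinuation visit: "except for end of treatment (ETD) visit".
- **Follow-up.** Protocol 9.1.1 asks participants who stop before Week 12 to continue to Week 12. SAP 2.5.1.3 uses their scores as observed.

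**The concern.** The order of events matters. Suppose a participant stops study drug at Week 5, stays in the diary and starts omalizumab at Week 6. If end of treatment means that participant's own stopping date, Table 6-3 is not breached. No deviation need be raised, and the only trigger for the composite rule may never fire. The Week 12 score on omalizumab then counts as treatment-policy data, although the estimand treats this intake as an unfavourable outcome.

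The same unflagged score feeds the ISS7, HSS7 and UAS7 responder analyses. It can also affect other participants. Where retrieved data are judged adequate, SAP 2.5.1.4 says that "if sufficient RDO data, missing data will be imputed using MI based on observed RDO data in the corresponding active arm". Step 3 of that section removes post-event values before imputation, but only for participants already identified.

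No planned analysis would reveal the omission. The sensitivity analysis changes only the imputed value. The supplementary estimand changes the strategy but refers back to 2.5.1.3 for data handling.

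**Working it through.** **Step 1: the plan's own figure.** SAP 3.1 gives 270 and 135 evaluable participants, a UAS7 difference of 10 and SD 12, "assuming type I error 0.025 (one-sided", and states "this gives a nominal power of more than >99" per cent.

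- SE = 12 × √(1/270 + 1/135) = 1.265
- 10 / 1.265 = 7.91, and 7.91 − 1.96 = 5.95
- Power = Φ(5.95), above 99.99%. The stated figure reproduces.

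**Step 2: who is exposed.** The gap needs study drug stopped first and the new drug started afterwards.

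| Drug class | Ban that ends at end of treatment | Ban without that limit | Window that counts |
|---|---|---|---|
| Urticaria biologics | Table 6-3 | none found | any time before Week 12 |
| Cyclosporin | Table 6-3 | none found | Weeks 8–12 |
| Systemic corticosteroid, not for urticaria | Table 6-3 | none found | Weeks 8–12 |
| Corticosteroid for urticaria | Table 6-3 | Protocol 6.2.4, until Week 12 | Weeks 8–12 |

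The last row stays prohibited after early stopping. The gap is clearest in the first two.

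**Step 3: size.** Let sP and sA be the shares of the placebo and active arms with an unflagged event, and y their observed Week 12 UAS7. Recoding them to 42 changes the benefit (placebo minus active) by

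(sP − sA) × (42 − y).

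The documents give none of these inputs. I assume shares of 0 to 5% and y from 6 to 20, so 42 − y runs from 22 to 36.

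| sP | sA | y = 20 | y = 6 |
|---|---|---|---|
| 2% | 0 | 0.02 × 22 = +0.44 | 0.02 × 36 = +0.72 |
| 5% | 0 | +1.10 | +1.80 |
| 5% | 2% | 0.03 × 22 = +0.66 | 0.03 × 36 = +1.08 |
| equal | equal | 0 | 0 |
| 2% | 5% | −0.66 | −1.08 |
| 0 | 5% | −1.10 | −1.80 |

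A positive value means that leaving the events unflagged understates the benefit; a negative value means that it overstates it. These are direct effects on the difference in means and leave out any carry-over through imputation. For the responder endpoints, one unflagged participant who meets the threshold adds 1/150 = 0.67 percentage points to placebo or 1/300 = 0.33 to active.

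**Step 4: power after recoding.** I assume Week 12 means of 12 and 22, SD 12, and 300 + 150 analysed. Power rounds to 1.0000 in every row above. In a deliberately extreme case (10% of active, none of placebo), the active mean becomes 0.9 × 12 + 0.1 × 42 = 15.0, the difference is 7.0 and power is 0.9997.

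**The case against.** The strongest objection is that the scope of M-COMD03 and M-COMD04 cannot be seen. The footnote to SAP Table 5-1 takes deviation codes from the edit check specifications, which are a separate document. The wording beside the biologics code is time-based, so the code may already cover everyone up to Week 12. End of treatment could also mean the planned 52 weeks; the SAP's use of the phrase for the early-discontinuation visit is a loose label, and its own table key spells ETD out as early treatment discontinuation. These points stand. A reader might infer that such use will certainly go undetected, or that the SAP defines the term. The documents support neither.

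A reader might also infer that the ban lapses for all three drug classes. It does not: Protocol 6.2.4 keeps corticosteroids for urticaria prohibited before Week 12. Cyclosporin or steroids taken before Week 8 are treatment policy by design. Where steroids or cyclosporine begin on treatment and lead to stopping, the prohibited use comes first and a deviation exists.

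Finally, the planned 10% drop-out does not size the affected group. It is used to reduce the evaluable numbers, whereas these participants must still have a Week 12 score. Equal shares in the two arms cancel.

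What remains is that the rule depends on an external list, and that the footnote calls for the latest version of that list at the time of analysis. Nothing in the SAP says that detection is independent of treatment status.

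**Conclusion.** The point holds as a possible gap between the estimand and its implementation. For biologics before Week 12, and for cyclosporin and non-urticaria systemic corticosteroids in Weeks 8 to 12, use that starts after study drug is stopped may carry no deviation and be analysed as ordinary retrieved data. Whether it would be missed depends on code definitions and on a term that the documents do not settle.

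On the assumed shares and scores, the UAS7 difference moves by 0 to about 1.8 points against a planned 10. The direction depends on which arm has more such use. It would be wrong to read this as a threat to power or as a bias of known sign. The matter is fidelity to the estimand, and it is worth correcting because the correction is cheap.

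**What to change.** In SAP 2.5.1.3, identify event 3 from the coded concomitant-medication records: drug, systemic route, start and stop dates. Apply this to every FAS participant up to the Week 12 score, whatever the study-treatment status, and keep the deviation codes as a cross-check. Use the same flag in Steps 1 to 3 of SAP 2.5.1.4 and in the sensitivity, supplementary, co-primary and secondary analyses.

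Protocol Table 6-3 and Section 6.2.4 should be reconciled, and end of treatment defined. Which clinical rule applies is for the sponsor to decide.

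The cost is one derived flag and a medical review of corticosteroid records to exclude the topical and intranasal use that Table 6-3 permits. The SAP should also say in advance whether oral courses below that table's threshold for routine use count. No new data are needed: Protocol 6.2.1 requires all medication after enrolment to be recorded, and Protocol 9.1.1 continues collection after study treatment is stopped. Patient care does not change.

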2.5.1.4 Handling of missing values

Missing data imputation will be performed for the analyses when using statistical model.

Handling of missing RDO data

If no RDO data was collected after study treatment permanent discontinuation, missing data will be imputed based on the following rules:

- For participants in the active treatment arms, if sufficient RDO data, missing data will be imputed using MI based on observed RDO data in the corresponding active arm. If not feasible (e.g., very limited RDO data), missing data will be imputed based on observed data in the placebo arm under the assumption of jump to reference (J2R) using MI.
- For participants in the placebo arm, if sufficient RDO data, missing data will be imputed using MI based on observed RDO placebo arm data. If not feasible (e.g., very limited RDO data), missing data will be imputed using MI under the MAR assumption based on the observed placebo arm data.

Handling of other missing data

If there is any missing data prior to Week 12, the missing data will be handled following the MAR assumption.

The detailed steps for handling of the intercurrent events and analyses are described below.

Step 1: Identify the participants with intercurrent events.

Step 2: For participants with intercurrent event 1 (Discontinuation of study treatment prior to Week 12 due to any reasons), determine the imputation strategy based on the amount of RDO data.

- Calculate the percentage of RDO data available at Week 12 in participants with intercurrent event 1 by treatment group
- If $\geq 50\%$ of participants had RDO data at Week 12, consider RDO data is sufficient
- If $< 50\%$ of participants had RDO data at Week 12, consider RDO data is not sufficient

Step 3: Perform the missing data imputation.

- For participants with intercurrent event 3 (Intake of strongly confounding prohibited medication), set missing at all visits after the event
- Perform the missing data imputation under MI framework according to the imputation strategy on Step 2. At the same time, missing data imputation of other missing data (i.e., non RDO data) will also be performed. The details on MI are described in [Section 5.4.3](#)

- Replace the values at all visits after the intercurrent event 3 with the worst value

Step 4: Perform the analysis.

